2.5. Vitamin D Supplementation

Dietary vitamin D plays important role as an essential source for individuals who are unable to go outdoors frequently. Currently, the lack of availability of database on Vitamin D content in locally available food impedes the Vitamin D research. Hence, there has been no local data on vitamin D intake among Malaysian. As a result, assessment of vitamin D intake is crucial and serves as a basis to warrant vitamin D supplementation or fortification.

Health authorities in the European Union and the U.S. have set adequate intake levels of vitamin D between 400 and 600 IU/day for adults. With sun-deprived lifestyle resulting in low vitamin D synthesis in the body is the major factor for insufficient vitamin D status. Expert panels in vitamin D research have proposed 25(OH)D blood plasma level of above 75nmol/L as the optimal level. To achieve this level, supplementation studies showed that a vitamin D intake of at least 800 – 1000 IU/day is required by adults.

As based on studies, vitamin D supplementation has been estimated to prevent vitamin D deficiency in approximately 98% of general population (39). Both vitamin D supplementation and sunlight exposure have been shown to increase serum 25(OH)D levels in elderly. To protect against bone diseases and other kinds of degenerative and autoimmune diseases, adequate intake of vitamin D are very important. The Institute of Medicine (IOM) as well as the 2011 Food and Nutrition Board revised and recommended adequate intake of vitamin D up to age 70 is 600IU/day (40). Adults aged more than 70 years required 800IU/day. The upper limit (UL) for vitamin D has been revised and updated to 4,000IU/day. This dosage is defined as the highest level of daily consumption that causes no side effects in humans when used indefinitely without medical supervision (41).

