It has been suggested that amounts up to 4,000IU/day of vitamin D may be needed to maintain a healthy 25(OH)D level, an intake of 400IU/day may represent a minimum. There is no reported vitamin D toxicity from long-term exposure to sunlight and no published studies showing adverse effects from dietary intake of 10,000IU dosage. This dose had been set as the No Observed Adverse Effects Level (NOAEL). Doses of 4,000IU/day for 3 months and 50,000IU/week for 2 months have been administered without toxicity (39). The European food safety authority and the US health authority have set 4000 IU/day of vitamin D as the tolerable upper intake level for adolescents and adults.

CHAPTER 3: RESEARCH OBJECTIVES AND HYPOTHESIS

Objectives

1. To determine the efficacy of vitamin D supplementation on plasma 25-hydroxyvitamin D [25(OH)D] and intact parathyroid hormone (PTH) concentrations after daily intake of supplements containing 500 mg calcium with either 0 IU, 600 IU, 1200 IU or 4000 IU vitamin D for 16 weeks.
2. To assess the influence of key covariates, namely sun exposure, vitamin D dietary intake and body mass index status on plasma 25-hydroxyvitamin D [25(OH)D] and intact parathyroid hormone (PTH) of the study participants at baseline and at 16 weeks of supplementation.

Hypothesis

1. H_0 : No significant differences in mean plasma 25-hydroxyvitamin D [25(OH)D] concentrations of participants consuming daily 500 mg calcium and vitamin D supplements at 0 IU, 600 IU, 1200 IU or 4000 IU for 16 weeks
2. H_0 : No significant differences in mean plasma intact parathyroid hormone (PTH) concentrations of participants consuming daily 500 mg calcium and vitamin D supplements at 0 IU, 600 IU, 1200 IU or 4000 IU for 16 weeks
3. H_0 : No significant influence of sun exposure duration, dietary intake of vitamin D and body mass index on plasma 25-hydroxyvitamin D [25(OH)D] and intact parathyroid hormone (PTH) of the study participants at baseline and at 16 weeks of supplementation

CHAPTER 4: METHODOLOGY

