4.4. Intervention

a) Socio-demographic form and anthropometry measurements

A short questionnaire enquiring socio-demographic characteristics, medical history, and usage of supplementations will be given and self-administered by the participants. This served as the first-line screening of participants to confirm that the participants are free from any medications or supplementations that are known to interfere with vitamin D or

calcium metabolism. Anthropometric measurements of weight, height and waist circumference will be measured. The weight of participants will be measured using TANITA digital scale. Participants will be asked to stand on the middle of the weighing scale with barefoot, head looking straight, arms by the side and with light clothing. Then the weight will be recorded and two measurements will be taken to obtain mean body weight. The height will be measured using SECA microtoise. The microtoise will be placed to a smooth surface wall. Then, it will be calibrate until the reading is 0 when pulled on the floor surface. Similar to measuring the weight, participants are required to stand with barefoot, feet with 'v' shape lean against the wall with the heels touching the wall, head placed in Frankfurt Plane and hand by the side. Two measurements will be taken to obtain mean height. By using the mean weight and height, BMI will be calculated to determine the BMI classification of the participants. The waist circumference will be measured using a measuring tape. With the subject in standing position, it will be measure midway between the lowest rib margin and the superior border of iliac crest.

b) To assess vitamin D intake using repeated 24-hour dietary recall

A 2-days 24-hour Diet Record (include 1 weekday, and 1 weekend) will be collected. Researcher will clarify the diet record with the participants upon collection. To allow the participants estimate on portion sizes correctly, photography tools or household measurement tools will be used during the clarification. This is to prevent any under-estimation or over-estimation of portion sizes which may affect the results of the data.

c) To assess sunlight exposure by using Sun Exposure Questionnaire

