The sunlight exposure of participants will be determined using a self-administered Sun Exposure Measurement Questionnaire (SEM-Q). It is a validated questionnaire widely used in other countries. Data collected from sunlight exposure measurement questionnaire (SEM-Q) in this study will be correlated with serum vitamin D.

d) Vitamin D supplementation and blood sample

Participants will be randomly divided into groups of 4 for a 16 weeks vitamin D supplementation. One of the group acts as a controlled and the other 3 grouping will be given different amount of vitamin D supplementation of 600IU/day, 1200IU/day and 4000

IU/day respectively. All groups' supplementation included 500mg/day of calcium. Blood collection will be conducted before supplementation as a baseline data, and after 16 weeks of supplementation. The baseline blood draw before supplementation served as the second-line screening of participants. The baseline blood draw served to provides researcher the basal serum 25(OH)D of participants and to exclude any hypo- or hyperthyroidism if detected. Blood drawing will be conducted by trained physicians or phlebotomists after an overnight fast. Blood sample of 5ml will be collected. The serum will be spin down, extracted and stored at -80°C until being analyzed. The serum 25(OH)D, and serum PTH will be analyzed. Serum vitamin D and PTH will be assayed using Centaur Analyser.

The supplements are provided by Fiatec Bioactive Sdn Bhd, Malaysia; where the raw ingredients are imported from DSM Nutritional Products. The products are prepared and packed into vegetable capsules, and will be analyze each to contain at least 90% of the required dosage amount. Vitamin D classification is categorized based on the recommendation of IOM. Serum 25(OH)D level lower than 30nmol/L considered as vitamin D deficiency; and level between 30-50nmol/L considered as vitamin D insufficiency (40). This part of the study is to determine the amount of vitamin required to provide optimum level of PTH, which in turns serves to indicate optimum absorption of calcium.

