4.5. Sample size

Calculation of sample size is done with the statistical power analysis program, G*Power 3. It covers wide statistical tests and provides improved effect size calculators (43). By obtaining the last 100 data on PTH values from local research data lab, the median for 12.5, 37.5, 62.5, 87.5th percentiles and overall standard deviation (SD) were obtained. The effect size is obtained by putting in the median and SD values into the G*Power program. Using G-power with 0.7597 (effect size), a power of 0.99 and alpha significance of 0.05, the total sample size is 48 subjects.

Hence, in consideration of the research requires follow-up of 16 weeks, with a 30% possibility of dropout rate and a various conditions of exclusion criteria, a sample size of 120 participants would be needed for invitation to the study.

[figure not shown]

Diagram 1: Screenshot of Sample Size Calculation using G-Power

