4.6. Randomisation: sequence generation

Stratified random sampling method shall be used as it allows equal distribution among each 3 ethnics as well as equal distribution for 4 supplementation groups. Each participant is masked with study code, and only the primary researcher has the master key list. Computer generated randomization of sampling into groups of four shall be used. The sample size will be divided into four groups: Placebo, 600IU/day, 1200IU/day and 4000IU/day. The divided group will then further divided equally into three ethnics group (Malays, Chinese, and Indian). The sampling method is illustrated as below:

[figure not shown]

Diagram 2: Illustration of stratified sampling method

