4.9. Blinding

Blinding will be strictly maintained by emphasising to intervention participants that each supplement capsules adheres to healthy and safety principles. Except for interventionist (primary researcher), investigators and participants are kept blind to supplementation assignment.

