4.11. Statistical methods

The dietary intakes collected from the repeated 24-hour diet recall will be entered. Using the database in Nutrient Composition of Malaysian Foods (1997) and Singapore Nutrient Composition of Foods (2003), all participants' nutrients intake will be analysed. The collected data will be converted into energy and nutrients intake using Nutritionist Pro Diet Analysis Software (NutriPro Software). Further analysis of data obtained will be carried out using Statistical Package for the Social Sciences (SPSS) version 22.0. The mean, standard deviation, and/or median, inter-quartile range will be calculated to describe the demographic background of the participants and nutrients intakes from the 24-hr diet record. Data obtained will be checked for distribution pattern, whether it is normally distributed or skewed. Analysis of covariance (ANCOVA) will be used to compare between the trial groups. To determine the relationship between several independent variables and a dependant variable, multiple regressions will be used. Bland-Altman will be used to analyze the agreement of variables. The significance level is set at $p < 0.05$.

References:

- [1] TJ Green, CM Skeaff, JEP Rockell, *et al.* Vitamin D status and its association with parathyroid hormone concentrations in women of child-bearing age living in Jakarta and Kuala Lumpur. *Eur J Clin Nutr* 2008; 62: 373-378.
- [2] Michael F. Holick. Vitamin D: A Millennium Perspective. *J Cell Biochem* 2003; 88: 296-307.
- [3] Joseph E Zerwekh. Blood biomarkers of vitamin D status. *Am J Clin Nutr* 2008; 87(suppl): 1087S-91S.
- [4] Michael F. Holick. High Prevalence of Vitamin D Inadequacy and Implications for Health. *Mayo Clin Proc.* 2006; 81(3): 353-373.
- [6] Geok L Khor, Winnie SS Chee, Zalilah M Shariff, Bee K Poh, Mohan Arumugam, Jamalludin A Rahman, Hannah E Theobald. High prevalence of vitamin D insufficiency and its association with BMI-for-age among primary school children in Kuala Lumpur, Malaysia. *BMC Public Health* 2011; 11: 95.
- [7] Chin KY, S Ima-Nirwana, Suraya Ibrahim *et al.* Vitamin D Status in Malaysian Men and Its Associated Factors. *Nutrients* 2014; 6: 5419-5433.
- [8] Nidhi Malhotra and Ambrish Mithal. Vitamin D status in Asia. International Osteoporosis Foundation (IOF).

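### The plan records no adverse events or withdrawal reasons and summarises neither by arm, so the trial as written would yield no harms data by vitamin D dose

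*Combined protocol and SAP*

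**What the plan says.** All references are to the combined protocol and SAP.

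- **Follow-up (4.4(d)).** Women take capsules daily for 16 weeks at 0, 600, 1200 or 4000 IU, with 500 mg calcium in every arm. On timing: "Blood collection will be conducted before supplementation as a baseline data, and after 16 weeks of supplementation". The assays are 25(OH)D and PTH. No other follow-up time is named.
- **Analysis (4.11).** "Analysis of covariance (ANCOVA) will be used to compare between the trial groups". The section also plans descriptive summaries of demographics and nutrient intake, multiple regression and Bland-Altman analysis.
- **Dropout (4.5).** The 120 invitations are justified "with a 30% possibility of dropout rate and a various conditions of exclusion criteria".
- **Dose background (2.5).** Authorities "have set 4000 IU/day of vitamin D as the tolerable upper intake level for adolescents and adults". Of that level the section says: "This dosage is defined as the highest level of daily consumption that causes no side effects in humans when used indefinitely without medical supervision". It also gives a NOAEL of 10,000 IU and reports that 4,000 IU/day for 3 months produced no toxicity.

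**The concern.** The trial gives healthy volunteers four different doses, the highest at the stated upper intake level. Section 4.4(d) says that the purpose is to find the amount of vitamin D that gives optimum PTH. Anyone weighing 1200 against 4000 IU/day from the results will ask whether the higher dose was tolerated as well as the lower.

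A team that follows this plan exactly would have nothing to answer with. Withdrawals per arm could be counted from missing week-16 samples, but the reasons for them would not be on file. Events among women who finish would not be on file either. Both could be sought afterwards, with some loss of recall.

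**Working it through.** This is an omission, so the main check is a reading of every methods section.

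**Step 1. Does any section provide for harms data?**

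| Section | Nearest content | Records events or withdrawal reasons? |
|---|---|---|
| 4.1 | Consent, voluntary participation | No |
| 4.2 | Eligibility, insurance cover | No; insurance collects no data |
| 4.3 | Setting and recruitment | No |
| 4.4(a) | Medical history and supplement use, as screening | No; it describes women before treatment |
| 4.4(b), (c) | Diet record, sun exposure questionnaire | No |
| 4.4(d) | Capsules, two blood draws, two assays | No |
| 4.5 | Dropout allowance | No; a number without reasons |
| 4.6 to 4.8 | Sequence, concealment, implementation | No |
| 4.9 | Reassurance to participants about the capsules | No; gives no way to record a problem |
| 4.10 | Comparison with a previous study | No |
| 4.11 | Analyses listed above | No harms or withdrawal summary |

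**Step 2. Could removed material explain the gap?** All eleven numbered sections are present. The two missing figures are captioned as the G*Power screenshot and the sampling illustration. The removed consent pages may hold a contact for side effects. A contact line would not amount to systematic collection in every arm, nor to a planned summary.

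**Step 3. The plan's own figure nearby.** Section 4.5 gives effect size f = 0.7597, alpha 0.05, power 0.99 and a total of 48. For a one-way ANOVA with four groups, the noncentrality is N × f².

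- N = 44: 44 × 0.7597² = 25.4, power 0.9885.
- N = 48: 48 × 0.7597² = 27.7, power 0.9938.

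So 48 is the smallest total with equal arms that reaches 0.99, and the figure reproduces. Allowing for dropout, 48 / (1 − 0.30) = 68.6, or 69 women, so the 120 invitations also cover exclusions. The calculation is built on PTH values. It is correct as far as it goes and has no bearing on harms.

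**Step 4. What could a harms table show?** The number randomised is not clear: section 4.5 gives 120 women for invitation, while section 4.3 can be read as 120 from each of three ethnic groups (360). If an arm of n women has no event of a given kind, the one-sided 95% upper bound on its rate is 1 − 0.05^(1/n).

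| Assumption | n per arm | Upper bound |
|---|---|---|
| 48 / 4 | 12 | 22.1% |
| 120 × 0.70 / 4 | 21 | 13.3% |
| 120 / 4 | 30 | 9.5% |
| 360 × 0.70 / 4 | 63 | 4.6% |
| 360 / 4 | 90 | 3.3% |

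A table from this trial could therefore describe common problems but could not exclude uncommon ones. As the plan stands, not even these modest statements could be made.

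**The case against.** The best case against the point has four parts.

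1. *No planned analysis fails.* The objectives and hypotheses concern 25(OH)D, PTH and three covariates, and no tolerability claim is promised. This stands in full and limits the weight of the point.
2. *Risk is low on the protocol's own text.* The upper level is defined for indefinite use, whereas this trial lasts 16 weeks; the NOAEL is 10,000 IU; and the top dose was given for 3 months, close to the trial's duration, without toxicity. This also stands. It lowers the expected number of events but supplies no record from this trial.
3. *The table would be imprecise.* True, as step 4 shows. That argues for a descriptive table without tests; it does not argue for collecting nothing.
4. *A form at week 16 misses women who withdraw.* Correct for many of them, so the fix needs a separate contact.

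Three stronger readings are tempting, and the documents do not support them.

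- A reader might infer that the 4000 IU arm is unsafe because diet, which section 4.4(b) measures ("A 2-days 24-hour Diet Record (include 1 weekday, and 1 weekend) will be collected"), adds to a supplement already at the upper level. The evidence in part 2 gives a small excess over 16 weeks little weight.
- A reader might infer that up to 30% of an arm could be leaving through intolerance. Section 4.5 calls 30% a possibility and uses it to size invitations. Nothing suggests that intolerance would approach it.
- A reader might infer that reasons could be sought only through an unblinded person, since "Each participant is masked with study code, and only the primary researcher has the master key list" and "Except for interventionist (primary researcher), investigators and participants are kept blind to supplementation assignment". Those sentences settle who holds the key and who is unblinded. They do not say who may contact participants, and section 4.4 already has other staff drawing blood. A blinded colleague could ask, with the key used only for linkage.

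**Conclusion.** The omission is real. Sections 4.1 to 4.11 plan no recording of adverse events or withdrawal reasons and no summary of either by arm. Its effect is narrow: the trial as written would have no harms data by dose. The 25(OH)D and PTH comparisons are untouched, no stated objective is lost, and nothing here says that the doses are unsafe or that staff would ignore a complaint.

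The omission has no numerical size, and the bounds in step 4 only show how little a table from arms of this size could exclude. The conclusion assumes that the removed pages contain no systematic collection plan. If they give only a contact for side effects, it is unchanged. This is a cheap improvement worth making, not a flaw in the efficacy design.

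**What to change.** 1. **Section 4.4(d), all women.** At the existing week-16 visit, give each woman a one-page self-administered form identified by study code, with one fixed question, for example: 'Since starting the capsules, have you had any new or worse health problem? If yes: what, when, and did you see a doctor or stop the capsules?' Record on the same form any event reported earlier.
2. **Women who stop or miss week 16.** A team member blind to allocation makes one phone or message contact to ask the reason and any health problem, and records 'not known' if she is not reached.
3. **Review.** A blinded investigator reads the forms as they arrive and sends serious or unexpected events to the ethics committee named in section 4.1 (IMU-JC).
4. **Section 4.11.** Add one descriptive table, without tests, of adverse events and of withdrawals with reasons by arm, with numbers randomised and numbers asked as denominators. Because every arm takes calcium, the table compares vitamin D doses only.

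The cost is a short amendment, handling and reading the forms, and a brief contact with each woman who withdraws. No new visit, blood draw or change of sample size is needed, and self-administered questionnaires are already in use. Recall over 16 weeks will miss some minor events, some reasons will stay unknown, and uncommon harms cannot be excluded.

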4.5. Sample size

Calculation of sample size is done with the statistical power analysis program, G*Power 3. It covers wide statistical tests and provides improved effect size calculators (43). By obtaining the last 100 data on PTH values from local research data lab, the median for 12.5, 37.5, 62.5, 87.5th percentiles and overall standard deviation (SD) were obtained. The effect size is obtained by putting in the median and SD values into the G*Power program. Using G-power with 0.7597 (effect size), a power of 0.99 and alpha significance of 0.05, the total sample size is 48 subjects.

Hence, in consideration of the research requires follow-up of 16 weeks, with a 30% possibility of dropout rate and a various conditions of exclusion criteria, a sample size of 120 participants would be needed for invitation to the study.

[figure not shown]

Diagram 1: Screenshot of Sample Size Calculation using G-Power

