4.3. Study setting

The target study population is group of academic and support staffs and universities students in Klang Valley. A total of 120 women subjects from each major race (Malay, Chinese, Indian) in Malaysia will be recruited.

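### The 0.99 power in section 4.5 rests on percentiles of one set of 100 laboratory PTH values, not on an expected PTH difference between doses, so it is unsupported.

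*Combined protocol and SAP*

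**What the plan says.** Section 4.5 is the only sample-size justification in the document. Its source is one set of laboratory records: "By obtaining the last 100 data on PTH values from local research data lab". From these, "the median for 12.5, 37.5, 62.5, 87.5th percentiles and overall standard deviation (SD) were obtained", and the values went into the G*Power effect-size calculator. The result is reported as: "Using G-power with 0.7597 (effect size), a power of 0.99 and alpha significance of 0.05, the total sample size is 48 subjects". Allowing for 30% dropout and for exclusions, the section concludes that "a sample size of 120 participants would be needed for invitation to the study". Section 4.3 gives recruitment differently: "A total of 120 women subjects from each major race (Malay, Chinese, Indian) in Malaysia will be recruited".

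The PTH null hypothesis in Chapter 3 is "No significant differences in mean plasma intact parathyroid hormone (PTH) concentrations of participants consuming daily 500 mg calcium" with vitamin D at 0, 600, 1200 or 4000 IU for 16 weeks. Section 4.4(d) states the aim again: "This part of the study is to determine the amount of vitamin required to provide optimum level of PTH". Section 4.11 gives the analysis: "Analysis of covariance (ANCOVA) will be used to compare between the trial groups". It names no covariate. Nowhere do the documents give an expected PTH mean by dose, an expected PTH difference, or a within-arm SD.

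**The concern.** The 12.5th, 37.5th, 62.5th and 87.5th percentiles are the medians of the four quarters of one distribution. Using them as four arm means amounts to sorting people by their PTH and treating the lowest to highest quarters as the four doses. Such groups differ by construction, whatever vitamin D does. The text describes no dose and no follow-up for these 100 records.

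A reader will take 0.99 as the chance of detecting a PTH dose effect, yet no dose effect entered the calculation. The risk lies mainly in interpretation. If the PTH comparison is not significant, the stated power would make that look like strong evidence that dose does not matter, and the figure cannot support that reading. The calculation does not address 25(OH)D, and nothing here concerns power for 25(OH)D.

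**Working it through.** **Inputs from the documents.** Effect size 0.7597, power 0.99, alpha 0.05, total 48, dropout 30%, 120 invited (section 4.5); four equal groups (section 4.6); 120 from each of three ethnic groups (section 4.3); ANCOVA (section 4.11).

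**Assumptions, because the documents give no figure.** Baseline to week-16 PTH correlation (rho) of 0.5 or 0.7; evenly spaced arm means; an illustrative 0.8 SD difference between extreme arms. SD below means the unadjusted within-arm SD of week-16 PTH.

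**1. Reproduce the plan's figure.** Four-group F test: numerator df 3, denominator df N − 4, noncentrality N·f².
- N = 48: noncentrality 48 × 0.7597² = 27.70, power 0.994.
- N = 44: power 0.988.

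So 48 is the smallest multiple of four that reaches 0.99. This supports reading 0.7597 as Cohen's f for four groups.

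**2. Apply the recipe where there is no treatment.** f = (SD of the four percentiles) / (overall SD). For a standard normal variable the percentiles are −1.150, −0.319, 0.319 and 1.150:

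f = √[(2 × 1.150² + 2 × 0.319²)/4] = 0.844.

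Results for other shapes, and for simulated sets of 100 records from one population (20,000 runs):

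| Shape | Theoretical f | Median f, 100 records | 95% range |
|---|---|---|---|
| Normal | 0.844 | 0.83 | 0.74–0.92 |
| Log-normal, log-SD 0.4 | 0.781 | 0.78 | 0.63–0.90 |
| Log-normal, log-SD 0.5 | 0.747 | 0.75–0.76* | 0.57–0.89 |
| Log-normal, log-SD 1.0 | 0.503 | about 0.57 | 0.28–0.81 |

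*Depends on the SD convention (n or n − 1).

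The plan's 0.7597 lies inside every one of these ranges, and none of the simulated populations contains a dose effect.

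**3. What 0.7597 means if read as a dose effect.**
- Evenly spaced arms: the SD of four evenly spaced means with range 1 is 0.3727, so the extreme arms differ by 0.7597/0.3727 = 2.04 SD.
- Two arms against two: 2 × 0.7597 = 1.52 SD.
- Two extreme arms with the other two midway: 0.7597/√(1/8) = 2.15 SD.
- Share of PTH variance explained by dose: 0.7597²/(1 + 0.7597²) = 0.366, about 37%.

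**4. What the planned numbers can detect.** ANCOVA noncentrality is N·f²/(1 − rho²) with denominator df N − 5. The unadjusted f for 80% power is 0.498 at 48, 0.369 at 84 and 0.210 at 252; dividing by 0.3727 gives the extreme-arm difference.

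| Completers | Unadjusted | rho 0.5 | rho 0.7 |
|---|---|---|---|
| 48 | 1.34 SD | 1.16 SD | 0.96 SD |
| 84 (120 × 0.70) | 0.99 SD | 0.86 SD | 0.71 SD |
| 252 (360 × 0.70) | 0.56 SD | 0.49 SD | 0.40 SD |

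The 84 is an upper bound under the 120 reading, because exclusions also come out of the 120.

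**5. Illustration.** For an assumed 0.8 SD difference between extreme arms (f = 0.8 × 0.3727 = 0.298), power in the same column order is:
- 48 completers: 35%, 46%, 63%
- 84 completers: 60%, 74%, 90%
- 252 completers: 98% or more throughout

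**The case against.** The strongest reply is that the trial is not run at 48. Dropout alone would need 48/0.70 = 69 subjects, and section 4.5 invites 120. If section 4.3 means 120 per ethnic group, the total is 360, and about 252 completers would detect fairly modest differences. A poor effect-size input also does not bias the ANCOVA, the randomisation or the type I error. All of this is correct. It means that low power is not shown and that the trial need not be enlarged on this ground. It does not supply the missing PTH effect, so 0.99 still has no basis.

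Adjusting for baseline PTH would help. But section 4.11 names no covariate and no correlation is given, so that gain cannot be credited beyond the range shown.

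The simulations are illustrative, since the documents give neither the spread nor the shape of the 100 values. Strong skew gives a smaller typical f (about 0.57 at log-SD 1.0). They show only that 0.7597 can arise without treatment; the main point follows from the method as described.

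The G*Power screenshot is not available in the text reviewed. The test family is therefore inferred from the exact reproduction of 48, and the reading of the inputs rests on the wording of section 4.5.

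The conflict over 120 or 360 is a separate inconsistency. It matters here only because any replacement power statement needs a settled number.

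**Conclusion.** The concern holds. The arithmetic in section 4.5 is right, but 0.7597 measures between-person spread in one sample and is not an effect size for the PTH hypothesis. The stated 0.99 power is therefore unsupported, and section 4.5 must be corrected because it is the document's only sizing argument.

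Taken as a dose effect, the input would require extreme arms 1.52 to 2.15 SD apart, depending on the pattern of means. The difference detectable with 80% power runs from 0.99 to 0.71 SD at 84 completers and from 0.56 to 0.40 SD at 252, for evenly spaced arms and rho from none to 0.7. These figures describe sensitivity under stated assumptions. They are not estimates of this trial's power, because no plausible PTH effect is given.

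**What to change.** 1. Withdraw the 0.7597/0.99/48 statement.
2. Reconcile sections 4.3 and 4.5 on whether 120 is the total or the number per ethnic group, and state the number expected to complete after exclusions and dropout.
3. Then do one of the following:
   - (a) enter expected week-16 PTH means by dose and a within-arm SD, with their source, and recompute; or
   - (b) report the minimum detectable PTH difference under the planned ANCOVA, naming the covariate and the assumed correlation.
4. State that 25(OH)D was not used for sizing.

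Possible wording for (b), with 84 replaced by the reconciled number of completers:

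> With 84 completers, alpha 0.05 and 80% power, the four-arm PTH comparison detects a difference between extreme arms of 0.99 SD unadjusted, or of 0.86 or 0.71 SD if baseline PTH is the covariate and correlates 0.5 or 0.7 with week-16 PTH (assumed values; evenly spaced arm means; SD is the unadjusted within-arm SD). Exclusions after invitation would reduce the number of completers and raise these differences.

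The cost is a rewritten section 4.5, one G*Power rerun and a decision on the recruitment number. Correcting the statement needs no extra enrolment. The price is a less favourable stated power for PTH.
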